4.3. Protocol Deviations

Subjects who did not meet the eligibility criteria for study entry but randomized in the study, will be summarized regardless of whether they were exempted by the sponsor or not. The summary will present the number and percentage of subjects who did not meet at least 1 eligibility criterion and the number of subjects who did not meet specific criteria by treatment group based on the All Randomized Analysis Set. A by-subject listing will be provided for those subjects who did not meet at least 1 eligibility (inclusion or exclusion) criterion. The listing will present the eligibility criterion (or criteria if more than 1 deviation) that subjects did not meet and related comments, if collected.

Protocol deviations occurring after subjects entered the study are documented during routine monitoring. The number and percentage of subjects with important protocol deviations (IPDs) by deviation reason (as specified in the IPD plan) will be summarized by treatment group for the All Randomized Analysis Set. A by-subject listing will be provided for those subjects with IPD.

4.4. Assessment of COVID-19 Impact

This study was ongoing during the novel coronavirus (2019 nCoV [COVID-19]) pandemic which has caused a disruption in the regular visit schedules for this study. Some subjects were unable to attend onsite visits due to shelter in place guidelines, site closures, or other reasons. This section provides how special situations due to COVID-19 will be handled in the analysis.

4.4.1. Study Drug or Study Discontinuation Due to COVID-19

A by-subject listing of reasons for premature study drug or study discontinuation due to COVID-19 will be created.

4.4.2. Protocol Deviations Due to COVID-19

A by-subject listing of important protocol deviation related to COVID-19 and non-important protocol deviation related to COVID-19 will be provided.

4.4.3. Missed and Virtual Visits due to COVID-19

A by-subject listing of subjects with missed or virtual visits due to COVID-19 will be provided by subject ID number in ascending order.

Information regarding missed or virtual visits due to COVID-19 was collected as free text in the CRF comment fields. The determination of missing or virtual visits due to COVID-19 will be done using Natural Language Processing (NLP) to search the CRF comment fields. A detailed explanation of the algorithm is given in [Appendix 5](#).

4.4.4. Adverse Events due to COVID-19

AEs due to COVID-19 will be included in analyses of AE if applicable, which will be determined through COVID-19 standardized MedDRA queries (SMQ) broad search. A by-subject listing of AEs due to COVID-19 will be provided.

5. BASELINE CHARACTERISTICS

5.1. Demographics and Other Baseline Characteristics

Subject demographic variables and baseline characteristics will be summarized by treatment group and overall using descriptive statistics for continuous variables and using number and percentage of subjects for categorical variables. The summary of demographic and other baseline characteristics data will be provided for the Safety Analysis Set for the following:

- Age (on the first dose date of any study drug)
- Age group (< 65 years, ≥ 65 years)
- Sex at birth (male, female)
- Race
- Ethnicity (Hispanic or Latino, not Hispanic or Latino)
- Geographic region and country
- Weight (kg)
- Height (cm)
- Body mass index (BMI; in kg/m²)
- Smoking Status (non-smoker, former smoker or current smoker)

A by-subject demographic and other baseline characteristics listing, including the informed consent date, will be provided by subject ID number in ascending order.

5.2. Baseline Disease Characteristics

Baseline disease characteristics include:

- Concurrent use of csDMARD and/or apremilast at randomization (Yes or No) and daily or weekly dose taken at randomization by medication
 - Only csDMARD and/or apremilast medication records with a start date prior to randomization date and an end date on or after randomization date or missing will be used for counting the number of subjects with csDMARD and/or apremilast use at randomization.
 - Only csDMARD and/or apremilast medication records with a start date prior to randomization date and an end date on or after randomization date or missing that have a valid dose, dose unit, and dosing frequency will be used for summarizing daily or weekly dose taken at randomization.

- Oral Corticosteroids use on Study Day 1 (Yes or No) and daily dose taken on Study Day 1
 - Only oral Corticosteroid medication records with a start date prior to Study Day 1 and an end date on or after Study Day 1 or missing will be used for counting the number of subjects with oral Corticosteroid use on Study Day 1.
 - Only oral Corticosteroid medication records with a start date prior to Study Day 1 and an end date on or after Study Day 1 or missing that have a valid dose, dose unit, and dosing frequency will be used for summarizing daily dose taken on Study Day 1.
 - All oral Corticosteroid medications' doses will be converted to prednisone equivalent dose (conversion chart is in [Appendix 3](#)).
 - If multiple oral Corticosteroid medications are taken on Study Day 1, the total daily dose will be the sum of those medications' doses at Study Day 1 after conversion.
- Topical Corticosteroids use on Study Day 1 (Yes or No)
 - Only topical Corticosteroid medication records with a start date prior to Study Day 1 and an end date on or after Study Day 1 or missing will be used for counting the number of subjects with topical Corticosteroid use on Study Day 1.
- NSAIDs use on Study Day 1 (Yes or No)
 - Only NSAIDs medication records with a start date prior to Study Day 1 and an end date on or after Study Day 1 or missing will be used for counting the number of subjects with NSAIDs use on Study Day 1.
- Duration of PsA from diagnosis (years)
 - Calculated as $((\text{first dose date}) - (\text{date of initial diagnosis}) + 1 \text{ day}) / 365.25$. If the date of initial diagnosis is incomplete, then the following rules will be applied:
 - missing day: use the first of the month
 - missing month: use January
- Swollen joint count based on 66 joints (SJC66)
- Tender joint count based on 68 joints (TJC68)
- Swollen joint count based on 28 joints (SJC28)
- Tender joint count based on 28 joints (TJC28)
- HAQ-DI total score

- SF-36v2 physical component summary (PCS) score
- SF-36v2 mental component summary (MCS) score
- FACIT-Fatigue
- LDI: Leeds Dactylitis Index in subjects with dactylitis at Baseline
- SPARCC Enthesitis Index: Spondyloarthritis Research Consortium of Canada Enthesitis Index in subjects with enthesitis at Baseline
- LEI: Leeds Enthesitis Index in subjects with enthesitis at Baseline
- Patient's Global Assessment of Psoriatic Arthritis Pain Intensity (PGAPI) (by VAS)
- PASI: Psoriasis Area and Severity Index in subjects with psoriasis covering $\geq 3\%$ of the BSA at Baseline
- PhGAP: Physician's Global Assessment of Psoriasis in subjects with psoriasis covering $\geq 3\%$ of the BSA at Baseline
- mNAPSI: Modified Nail Psoriasis Severity Index in subjects with psoriatic nail involvement at Baseline
- PsAID-12: 12-item Psoriatic Arthritis Impact of Disease
- DAS28 (CRP): Disease Activity Score 28 by CRP
- DAPSA: Disease Activity in Psoriatic Arthritis
- PASDAS: Psoriatic Arthritis Disease Activity Score
- Tender dactylitis count (TDC) in subjects with dactylitis at Baseline
- Patients' global assessment of disease activity (PGADA)
- Physician's global assessment of disease activity (PhGADA)
- High-Sensitivity C-reactive Protein (hsCRP)
- hsCRP ($\geq 6\text{mg/L}$ or $<6\text{mg/L}$)

These baseline disease characteristics will be summarized by treatment group and overall using descriptive statistics for continuous variables and using number and percentage of subjects for categorical variables. The summary of these baseline characteristics will be provided for the Safety Analysis Set. No formal statistical testing is planned.

A by-subject listing of baseline disease characteristics will be provided by subject ID number in ascending order.

5.3. Medical History

Medical history collected at screening will be coded using the current version of Medical Dictionary for Regulatory Activities (MedDRA).

Medical history will be summarized by system organ class (SOC), preferred term (PT), treatment group, and overall. Subjects who report 2 or more medical history items that are coded to the same SOC and/or PT will be counted only once by the unique coded term in the summary.

The summary will be provided for the Safety Analysis Set. No formal statistical testing is planned.

A by-subject listing of medical history will be provided by subject ID number in ascending order.

6. EFFICACY ANALYSES

6.1. General Considerations

The primary analysis set for efficacy analyses will be the FAS, defined in Section 3.1.2.

Due to study early termination and insufficient number of subjects enrolled, all the hypothesis testings performed and p-values reported will be nominal, and, unless specified otherwise, all the confidence intervals will be calculated based on the nominal level of 95%. The results need to be interpreted with caution.

Efficacy analysis will be conducted on all available data during the Main Study phase (including data collected through the Week 16 visit after study drug discontinuation).

Estimands:

Treatment policy estimand is defined for the primary and key secondary as well as other secondary efficacy endpoints and will be the primary estimand for all the corresponding efficacy analyses:

- 1) Population: Subjects in the FAS.
- 2) Variable / endpoint: Primary and key secondary endpoints as well as other secondary endpoints (see details in subsequent Sections).
- 3) Strategy to address intercurrent events: include all on-study data regardless of protocol violations, use of rescue medication, change in background medication, and study drug discontinuation.
- 4) Population-level summary: treatment difference in the percentage of subjects meeting specific criteria for response defined by binary efficacy endpoints or mean treatment difference for continuous efficacy endpoints between each filgotinib group and placebo group or adalimumab group if applicable.

Selection of Efficacy Data in the Event of Multiple Records in an Analysis Visit Window

If multiple valid, nonmissing efficacy measurements exist in an analysis window, records will be chosen based on the following rules if a single value is needed:

- The record closest to the nominal day for that visit will be selected.
- If there are 2 records that are equidistant from the nominal day, or more than 1 record (with time known) on the selected day, the latest record will be taken.
- If chronological order cannot be determined (e.g., more than 1 record on the same day with time missing), for any given subject, the worst outcome will be selected.

Calculation of Composite Endpoints

For the calculation of composite endpoints including DAS28(CRP), ACR20/50/70, MDA, VLDA, PASDAS, DAPSA, PsARC, we use the following steps unless otherwise specified:

- Step 1: Assign individual components to analysis visit windows defined in Section 3.7.2
- Step 2: Within each analysis visit window, select the component-level data based on the rules for selecting efficacy data as above
- Step 3: Calculate the composite endpoint based on the selected component-level data in Step 2.

Missing Data Consideration

Unless specified otherwise, below are the consideration for the missing data that will be used throughout the efficacy analyses:

Observed case (OC): Missing values remain missing. For the categorical composite endpoints, in the case that some components are missing, the composite endpoint assessment will be derived based on the nonmissing components. If nonmissing components are not sufficient to determine final composite endpoint, then the composite endpoint will be set as missing. For continuous composite endpoints, if any components are missing, the composite endpoints will be set as missing.

If a subject only has baseline measurements, OC analyses will not include this subject.

For subjects who were re-randomized, the baseline value for the LTE phase will be the last nonmissing measurement obtained on or prior to the first dose date of filgotinib in the LTE. The change from baseline at analyses visits during LTE phase will be assessed from the re-randomized baseline of the LTE phase. The evaluation of response at analysis visits during LTE phase will be assessed from the re-randomized baseline of the LTE phase.

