3.7.2. Analysis Visit Windows

Subject visits might not occur on protocol-specified days. Therefore, for the purpose of analysis, observations will be assigned to analysis windows.

In general, the study baseline value will be the last nonmissing value on or prior to the first dose date of study drug.

For subjects who were re-randomized to LTE phase (placebo or adalimumab treated subjects), the re-randomized baseline will be the last nonmissing value obtained on or prior to the first dose date of any study drug for LTE.

For subjects enrolled under PA 1 who stayed in Main Study beyond Week 16 Visit, the analysis visit window will only be applied to the data up to Week 16 visit.

The analysis windows for joint count assessment, HAQ-DI including subject's pain assessment, Patient's Global Assessment of Disease Activity (PGADA), Patient's Global Assessment of Psoriatic Arthritis Pain Intensity (PGAPI), Physician's Global Assessment of Disease Activity (PhGADA), CRP, vital signs, weight, and safety laboratory data (lipid data excluded) are provided in [Table 3-1](#).

Table 3-1. Analysis Visit Windows for Joint Count Assessment, HAQ-DI, PGADA, PGAPI, PhGADA, CRP, Vital Signs, Weight, and Safety Laboratory Data (Lipid Data Excluded)

Analysis Visit	Nominal Study Day	Visit Window Study Day	
		Lower Limit	Upper Limit
Baseline	1	(none)	1
Week 2	15	2	22
Week 4	29	23	43
Week 8	57	44	71
Week 12	85	72	99
Week 16	113	100	Week 16 Visit Date – Study Day 1 + 1*
Analysis Visit	Nominal LTE Study Day	LTE Lower Limit	LTE Upper Limit
Week 18	15	2	22
Week 20	29	23	43
Week 24	57	44	71
Week 28	85	72	113
Week 36	141	114	183
Week 48	225	184	267
Week 60	309	268	351
Week 72	393	352	435
Week 84	477	436	519
Week 96	561	520	603
Week 108	645	604	687
Week 120	729	688	≥ 729

* For subjects who did not enter LTE phase, upper limit is “>= 113”; for subjects enrolled under PA1 who stayed in Main Study beyond Week 16, upper limit is 127.

The analysis windows for lipid data are provided in [Table 3-2](#):

Table 3-2. Analysis Visit Windows for Lipid Data

Analysis Visit	Nominal Study Day	Visit Window Study Day	
		Lower Limit	Upper Limit
Baseline	1	(none)	1
Week 16	113	2	Week 16 Visit Date – Study Day 1 + 1*
Analysis Visit	Nominal LTE Study Day	LTE Lower Limit	LTE Upper Limit
Week 48	225	2	393
Week 96	561	394	645
Week 120	729	646	≥ 729

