* For subjects who did not enter LTE phase, upper limit is “>= 113”; for subjects enrolled under PA1 who stayed in Main Study beyond Week 16, upper limit is 141.

The analysis windows for PhGAP data are provided in [Table 3-3](#).

Table 3-3. Analysis Visit Windows for PhGAP Data

Analysis Visit	Nominal Study Day	Visit Window Study Day	
		Lower Limit	Upper Limit
Baseline	1	(none)	1
Week 2	15	2	22
Week 4	29	23	43
Week 8	57	44	71
Week 12	85	72	99
Week 16	113	100	Week 16 Visit Date– Study Day 1 + 1*
Analysis Visit	Nominal LTE Study Day	LTE Lower Limit	LTE Upper Limit
Week 18	15	2	22
Week 20	29	23	43
Week 24	57	44	71
Week 28	85	72	113
Week 36	141	114	183
Week 48	225	184	309
Week 72	393	310	477
Week 96	561	478	645
Week 120	729	646	≥ 729

* For subjects who did not enter LTE phase, upper limit is “>= 113”; for subjects enrolled under PA1 who stayed in Main Study beyond Week 16, upper limit is 127.

The analysis windows for PASI including BSA, mNAPSI, SPARCC Enthesitis Index and LEI, LDI data are provided in [Table 3-4](#):

Table 3-4. Analysis Visit Windows for PASI including BSA, mNAPSI, SPARCC Enthesitis Index and LEI, LDI Data

Analysis Visit	Nominal Study Day	Visit Window Study Day	
		Lower Limit	Upper Limit
Baseline	1	(none)	1
Week 4	29	2	43
Week 8	57	44	71
Week 12	85	72	99
Week 16	113	100	Week 16 Visit Date – Study Day 1 + 1*
Analysis Visit	Nominal LTE Study Day	LTE Lower Limit	LTE Upper Limit
Week 20	29	2	43
Week 24	57	44	71
Week 28	85	72	113
Week 36	141	114	183
Week 48	225	184	309
Week 72	393	310	477
Week 96	561	478	645
Week 120	729	646	≥ 729

* For subjects who did not enter LTE phase, upper limit is “>= 113”; for subjects enrolled under PA1 who stayed in Main Study beyond Week 16, upper limit is 127.

The analysis windows for FACIT-Fatigue, SF-36v2, PsAID-12 data are provided in [Table 3-5](#)

Table 3-5. Analysis Visit Windows for FACIT-Fatigue, SF-36v2, PsAID-12 Data

Analysis Visit	Nominal Study Day	Visit Window Study Day	
		Lower Limit	Upper Limit
Baseline	1	(none)	1
Week 4	29	2	71
Week 16	113	72	Week 16 Visit Date – Study Day 1 + 1*
Analysis Visit	Nominal LTE Study Day	LTE Lower Limit	LTE Upper Limit
Week 48	225	2	393
Week 96	561	394	645
Week 120	729	646	≥ 729

* For subjects who did not enter LTE phase, upper limit is “>= 113”; for subjects enrolled under PA1 who stayed in Main Study beyond Week 16, upper limit is 141.

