6.4.1. Definition of Other Secondary Endpoints

6.4.1.1. Tender Dactylitis Count (TDC)

Tender score (0 = no tenderness, 1 = tender, 2 = tender and wince, 3 = tender and withdraw) is collected for Dactylitis Assessments on the Dactylitis Score Sheet that was used for calculation of LDI total score.

Tender dactylitis count (TDC) equals the number of tender fingers and toes (tender score >0). For subjects with dactylitis status absent for all the fingers and toes, the TDC will be set as 0. This score is used as a component of the PASDAS.

If there are missing fingers or toes, then the missing count for those fingers or toes will not be included in the TDC.

6.4.1.2. Psoriatic Arthritis Disease Activity Score (PASDAS), PASDAS Low Disease Activity (LDA) and PASDAS remission

$$\text{PASDAS} = \left[0.18 \times \sqrt{\text{PhGADA}} + 0.159 \times \sqrt{\text{PGADA}} - 0.253 \times \sqrt{\text{PCS}} + 0.101 \times \ln(\text{SJC66} + 1) + 0.048 \times \ln(\text{TJC68} + 1) + 0.23 \times \ln(\text{LEI} + 1) + 0.377 \times \ln(\text{TDC} + 1) + 0.102 \times \ln(\text{CRP} + 1) + 2 \right] \times 1.5$$

where

PhGADA = Physician's Global Assessment of Disease Activity (0 – 100 VAS);

PGADA = Patient's Global Assessment of Disease Activity (0 – 100 VAS);

PCS = Physical Component Score of the SF-36;

LEI = Leeds Enthesitis Index, derived from the enthesitis assessments;

TDC = Tender Dactylitis Count from the LDI;

CRP is in the unit of mg/L.

A lower score indicates better function.

If a subject did not have dactylitis at baseline and hence no dactylitis assessments are collected post-baseline, then it is assumed that TDC = 0 at baseline and all post-baseline visits for calculating PASDAS.

If a subject did not have enthesitis at baseline and hence no enthesitis assessments are collected post-baseline, then it is assumed that LEI = 0 at baseline and all post-baseline visits for calculating PASDAS.

If any of the components is missing, then PASDAS remains missing.

PASDAS LDA is defined as $PASDAS \leq 3.2$; PASDAS remission is defined as $PASDAS \leq 1.9$.

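### Assigning PASDAS components to visits before combining them discards complete early-termination scores and can mix dates weeks apart; derive the score from one visit first

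*SAP*

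**What the plan says.** SAP 6.1 (Calculation of Composite Endpoints) names PASDAS among the composites and gives three steps. The first is "Step 1: Assign individual components to analysis visit windows defined in Section 3.7.2". The second picks one record per component within each window, using the rule "The record closest to the nominal day for that visit will be selected". The third is "Step 3: Calculate the composite endpoint based on the selected component-level data in Step 2". Another section may override these steps, but SAP 6.4.1.2, which defines PASDAS, does not. It adds: "If any of the components is missing, then PASDAS remains missing".

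The PASDAS components are windowed in three places in SAP 3.7.2:

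- SJC66, TJC68, PGADA, PhGADA and CRP use Table 3-1.
- LEI, and LDI as the source of TDC, use "Table 3-4. Analysis Visit Windows for PASI including BSA, mNAPSI, SPARCC Enthesitis Index and LEI, LDI Data".
- PCS comes from SF-36v2, which has its own limits: "The analysis windows for FACIT-Fatigue, SF-36v2, PsAID-12 data are provided in" Table 3-5.

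SAP 3.7.2 applies the windows to all on-study efficacy data and gives no separate rule for ET visits. Protocol Appendix 2 schedules SF-36v2 in the Main Study only at Day 1, Week 4, Week 16 and ET, and the ET visit collects every PASDAS component. Protocol 6.3.1 places the ET visit of a subject who leaves before Week 16 within 7 days of leaving, so it can fall on almost any study day.

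**The concern.** Components measured on the same day can receive different visit labels. PASDAS then cannot be formed at any visit, although everything needed was collected together. In a narrower case, PASDAS is formed from records that are weeks apart and do not describe one disease state.

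The same tables also give Week 16 two meanings among the key secondary endpoints. SF-36 PCS and FACIT-Fatigue can count as Week 16 from Day 72, whereas LEI, LDI, PASI75 and MDA start at Day 100.

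ET visits matter here because the sponsor stopped the study after 67 subjects and only 13 entered the LTE (SAP 1.3). If the 2:2:1:2 ratio held (an assumption), the arms have about 19, 19, 10 and 19 subjects, so one relabelled or lost value is roughly 5% to 10% of an arm.

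**Working it through.** **Inputs.** Window limits from SAP Tables 3-1, 3-4 and 3-5; Steps 1-3 and the selection rule from SAP 6.1; the missing-component rule from SAP 6.4.1.2; visit schedule and the ±3-day window from Protocol Appendix 2.

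**Reproducing the plan's limits.** Each upper limit is the midpoint of adjacent nominal days, and the next window starts one day later.

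- Table 3-1: (15+29)/2 = 22; (29+57)/2 = 43; (57+85)/2 = 71; (85+113)/2 = 99.
- Table 3-4 has no Week 2; its limits are 43, 71 and 99.
- Table 3-5 has only Weeks 4 and 16: (29+113)/2 = 71, so Week 16 starts on Day 72.

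These are the printed Main Study limits. Day 72 follows the rule used throughout.

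**Labels for a complete component set collected at one ET visit.**

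| ET day | Joint counts, PGADA, PhGADA, CRP | LEI, TDC | PCS | Can the ET set form a PASDAS? |
|---|---|---|---|---|
| 2-22 | Week 2 | Week 4 | Week 4 | No |
| 23-43 | Week 4 | Week 4 | Week 4 | Yes |
| 44-71 | Week 8 | Week 8 | Week 4 | No |
| 72-99 | Week 12 | Week 12 | Week 16 | No |
| 100 on | Week 16 | Week 16 | Week 16 | Yes |

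Split days: 21 + 28 + 28 = 77 of the 98 calendar days from Day 2 to Day 99. SAP 6.4.1.2 sets TDC and LEI to 0 for subjects without dactylitis or enthesitis at baseline. That does not repair the split, because PCS and joint counts differ on all 77 days. On Days 2-22, Table 3-4 adds to the split as well.

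**Tracing cases through Steps 1-3** (earlier visits on nominal days).

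- ET on Day 60, Week 4 SF-36 present: the Day 29 PCS is nearer to nominal and is selected. Week 4 PASDAS is intact; the Day 60 score is not formed.
- ET on Day 60, Week 4 SF-36 missing: the Week 4 PASDAS uses Day 29 joint counts, CRP, LEI and TDC with Day 60 PCS.
- ET on Day 85: joint counts, CRP, LEI and TDC go to Week 12 and PCS to Week 16. PASDAS is missing at both.
- ET on Day 105: everything is Week 16 and PASDAS is formed.

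**Size of the date gap in the mixed case.** From a Day 29 visit: 44 - 29 = 15 days to 71 - 29 = 42 days. Allowing the ±3-day visit window (Days 26-32): 44 - 32 = 12 to 71 - 26 = 45 days.

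**The two meanings of Week 16.** The earliest Week 16 PCS or FACIT-Fatigue is 113 - 72 = 41 days before nominal. The earliest Week 16 LEI, LDI, PASI75 or MDA is 113 - 100 = 13 days before nominal.

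**Subjects at risk.** 67 - 13 = 54 subjects did not enter the LTE. Some of them completed the Main Study, and no count of ET visits by day is given, so the range is 0 to 54.

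**Check of the fix.** If PASDAS is computed within a visit and then windowed with Table 3-5, no ET day from 2 to 99 is split (0 of 98). The score always carries the same label as its PCS, and no score mixes dates.

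**The case against.** The strongest reply is that little usable information is lost. SF-36 is scheduled only at Weeks 4 and 16 after baseline, so PASDAS has no scheduled value at Weeks 2, 8 or 12. Labelling recovered scores with Table 3-1 would fill those visits almost entirely with early leavers. That objection stands, and it is why the fix below uses Table 3-5.

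Three other points also stand:

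- A reader might infer from 77 of 98 days that most ET scores are lost. That figure is a share of calendar days, not of subjects or data. The documents do not say when ET visits occurred. Subjects who stop drug but stay until Week 16 have the ET visit in place of the Week 16 Visit (Protocol 6.3.1), where all tables agree.
- The mixed-date Week 4 score is not routine. It needs a missed Week 4 SF-36 as well as an ET visit on Days 44-71.
- A reader might call the Day 72 limit a mistake. It is the midpoint for an instrument with two post-baseline visits, and it matters only when no SF-36 lies nearer Day 113. Moving it to Day 100 would drop on-study data that the treatment policy approach means to keep.

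The by-subject listings in SAP 6.4.2 also preserve the raw components. None of this answers the main point: as written, the steps withhold a score that the data support, and in one case build a score across visits.

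**Conclusion.** The point holds as a derivation fault of limited reach. For ET visits on Days 2-22, 44-71 and 72-99, a complete component set yields no PASDAS. With a missed Week 4 SF-36, an ET visit on Days 44-71 can yield a Week 4 PASDAS joining records up to 42 days apart (both on a nominal Day 29 visit; up to 45 with visit tolerance). Scheduled Week 4 and Week 16 visits inside their visit windows are not affected by the split.

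Between 0 and 54 subjects are affected. PASDAS, its LDA and its remission are other secondary endpoints with no planned test, and all p-values in this SAP are nominal (SAP 3.4). The documents do not support a reading that the primary endpoint is affected, or that the Week 16 PCS and FACIT-Fatigue results are invalid. For those two endpoints the issue is disclosure: the reader should know how many Week 16 values were taken on Days 72-99.

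**What to change.** 1. In SAP 6.1 or 6.4.1.2, state that PASDAS is computed from components collected at the same visit, and that the finished score is then assigned with the limits of its least frequent component (Table 3-5: Week 4 is Days 2-71, Week 16 is from Day 72). The closest-to-nominal rule then chooses among finished scores. A Day 60 score still gives way to a Day 29 score where one exists.
2. Keep the Table 3-5 window. Report by arm how many Week 16 values of PCS, FACIT-Fatigue and PASDAS come from Days 72-99, and repeat the Week 16 summary without them. SAP 6.5 rules out sensitivity analyses, so this summary must be named there as an addition.
3. If the SAP is already final, record the rule in the CSR, as SAP Section 1 requires.

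The cost is SAP wording and a small amount of programming, with no new data. The downside is that a few ET scores will be labelled Week 16 up to 41 days early, under the convention that the SAP already applies to SF-36.
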